## 8.7.5 ADVERSE EVENT REPORTING

All AEs that occur during or after the Preoperative Visit through completion of study participation must be documented. Adverse events are collected from time of informed consent, and may be determined by evaluating the following in relation to the study subject:

- Observed or volunteered problems
- Complaints
- Physical signs and symptoms
- The occurrence of a medical condition during the study, which was absent at baseline
- The worsening of a baseline medical condition during the study

Each subject eye must be examined for the presence/absence of adverse events at all visits, whether scheduled or not. If an AE occurs, the first concern will be the safety and welfare of the subject; treatment should be provided as appropriate for the event.

AEs, regardless of causal relationship, must be assessed by the Investigator and recorded in the subject's CRF. AEs should be recorded in the form of a diagnosis, rather than signs and symptoms. Each AE must be described as ocular or non-ocular along with the following information: date of onset, date of resolution, severity, nature of the event (intermittent, continuous), action taken (none, medical and/or surgical), relationship to study device and surgical procedure, seriousness criteria and expectedness. Any medication or other intervention necessary for the treatment of an AE must be recorded on the appropriate eCRF. If the same type of AE occurs multiple times, each event should be recorded separately.

AEs will be documented beginning at the time of onset, and documentation must continue until recovery is noted. Events that are ongoing at the time of study exit should be followed until resolution or stabilization.

Ocular conditions or diseases noted during the Preoperative Visit that are chronic but stable and meet the inclusion/exclusions criteria should be recorded as Ocular History in the subject's case report form. The worsening of a preoperative condition or disease will be considered an AE. As applicable, signs and symptoms indicating a common underlying pathology should be noted as one comprehensive event.

---

#### 8.7.6 EXPEDITED ADVERSE EVENT REPORTING

Any ocular SAE or UADE, whether the event is expected or unexpected, ***must be reported to the Sponsor, or the Sponsor's designee, within 24 hours*** of the Investigator becoming aware of the event. Non-ocular SAEs must be reported within 7 days.

SAEs and UADEs must be recorded in the subject's eCRF. Information provided on the eCRF should be supplemented with hospitalization records, death certificate, clinic notes from specialists evaluating the subject's condition, etc., as applicable for the event. The urgency for reporting SAEs/UADEs is 3-fold:

- To facilitate discussion [and implementation, if necessary] by the Sponsor and the Investigator of appropriate follow-up measures.
- To facilitate Investigator reporting of unanticipated problems involving risk to human subjects to the IRB, and
- To enable the Sponsor to fulfill the reporting requirements to the appropriate regulatory authority.

It is the responsibility of the Investigator to promptly notify the IRB of SAEs per the IRBs reporting requirements. Investigators must report the occurrence of a UADE to their reviewing IRB as soon as possible, but no later than 10 working days after first learning of the event. The Sponsor must report the results of an evaluation of an UADE to FDA and all reviewing IRBs and participating investigators within 10 working days after the Sponsor first receives notice of the effect.

---

#### 8.7.7 ANTICIPATED ADVERSE EVENTS

As per ISO 11979-7 (2018) and *The American Academy of Ophthalmology Task Force Consensus Statement on Adverse Events with Intraocular Lenses*, the anticipated AEs associated with cataract

surgery and/or Toric IOL implantation that might reasonably be expected to occur in this study are listed below and include, but are not limited to, the following:

#### Intraoperative Adverse Events

- Anterior capsule tear
- Hyphema
- Vitreous prolapse
- Wound leak (positive Seidel)
- Posterior capsular rupture
- Choroidal detachment/hemorrhage
- Zonular dialysis
- Thermal injury (phaco burn)
- Iris or pupil damage

#### Postoperative Adverse Events

- Anterior uveitis (including iritis and iridocyclitis)
- Capsular block syndrome
- Choroidal detachment/hemorrhage
- Chronic anterior uveitis [anterior segment inflammation characterized by grade 1+ cell or greater (using the Standardization of Uveitis Nomenclature [SUN] criteria) that is persistent for greater than 3 months after surgery, or relapses in less than 3 months after discontinuation of therapy, or the subject is maintained on therapy for more than 3 months to control inflammation.] Note that any iritis present at the final visit is considered significant and should be counted as a 'persistent ISO SPE event'.
- Visually significant corneal edema [corneal swelling (stromal or epithelial) resulting in BCDVA of 0.3 logMAR or worse at Form 3 or later]. Note that any corneal stromal edema present at the final visit is considered significant and should be counted as a 'persistent ISO SPE event'.
- Clinically significant cystoid macular edema (CME) diagnosed by clinical exam and adjunct testing (e.g., OCT or other method), resulting in BCDVA of  $\leq 0.3$  logMAR at Form 3 or later
- Endophthalmitis (intraocular inflammation leading to diagnostic vitreous tap and use of intraocular antibiotics)
- Flat anterior chamber with lens/cornea touch or a shallow chamber with iridocorneal apposition without lens/cornea touch
- Anterior Capsular Contraction Syndrome (ACCS, Phimosis)
- Hypopyon
- Corneal endothelial damage
- Incorrect IOL power resulting in secondary surgical intervention
- Increased IOP (elevation of IOP  $\geq 10$  mmHg above the IOP measured at the Preoperative Visit to a minimum of 25 mmHg)
- Infectious keratitis
- IOL damage resulting in secondary surgical intervention

- IOL dislocation, tilt, decentration, luxation, rotation resulting in secondary surgical intervention
- Best-corrected distance visual acuity loss of 2 lines (10 letters) or more on the ETDRS chart measured at or after postoperative Form 4 compared to any prior postoperative visit
- Best-corrected distance visual acuity loss of 2 lines (10 letters) or more since the prior visit
- Mechanical pupillary block (A shallowing of the anterior chamber due to obstruction of aqueous humor flow from the posterior to anterior chamber through the pupil by the crystalline lens, vitreous face, or implanted device)
- Chronic pain in the study eye, per subjective patient reporting, graded as  $\geq 4$  on the standardized pain rating scale (from 0 to 10), present greater than 3 months postoperative
- Retained lens material
- Rhegmatogenous retinal detachment (RD) (partial or complete RD associated with retinal tear)
- Secondary IOL intervention (Exchange, Removal, or Reposition)
- Secondary surgical intervention (include, but are not limited to lens repositioning, lens replacement, vitreous aspiration, iridectomy for pupillary block, wound leak repair, and retinal detachment repair). It excludes posterior capsulotomies
- Synechiae formation
- Toxic anterior segment syndrome (TASS) (An acute, noninfectious inflammation of the anterior segment of the eye that starts within 24 to 48 hours after surgery, usually resulting in hypopyon and commonly presenting with corneal edema, and that improves with steroid treatment)

Investigators should accurately record the resolution status of all AEs, including all sequelae which could be on ocular structure or ocular (or visual) function.

Early, low grade anterior chamber cell/flare, corneal edema, and increase in IOP can often be considered normal or expected after IOL surgery. They do not need to be reported as adverse events if they occur prior to 1 week postoperatively if they meet the following criteria:

- Anterior chamber cells or flare of grade 2 or less that requires no change in standard postoperative medication regimen (if it persists to 1 week or more it should be reported as an adverse event);
- Corneal edema of grade 2 or less that does not reduce acuity to 0.3 logMAR (20/40) or worse and does not require any change in standard postoperative medication regimen (if it persists to 1 week or more it should be reported as an adverse event);
- Increased IOP that is  $<10$ mm Hg above baseline or is  $<25$ mmHg and requires no change in standard postoperative medications regimen or any other special treatment.

However, note that all secondary surgical interventions (and events that cause these interventions) and all events that have sequelae should be reported as adverse events, regardless of when they occur.

Note: Posterior capsular opacification (PCO) is NOT to be reported as an AE, per ISO 11979-7. YAG capsulotomies should be reported in the subject's case report form.

---

#### 8.7.8 DEVICE DEFICIENCIES

Device deficiencies related to the identity (e.g., labeling), quality, durability, reliability, safety, effectiveness, or performance of the study device must be reported to the Sponsor, or Sponsor's designee, within 7 days of the Investigator becoming aware of the deficiency. Device deficiencies must be recorded in the subject's case report form.

Device deficiencies will be categories as one of the following:

- **Device failure:** A device has failed if it is used according to the labeling, including without limitation, instructions for use, and applicable standards of medical practice but does not perform according to the labeling and negatively impacts the treatment.
- **Device malfunction:** A device malfunction is a change in the function of the device that is not described in the labeling and that may or may not affect device performance.
- **Device misuse:** A misused device, i.e., one that is not used by the Investigator (in the study) in compliance with applicable standards of medical practice, including without limitation, those described in the instructions for use and labeling, will not be considered a malfunction.
- **Other:** must be described by the Investigator

## 9 STATISTICAL CONSIDERATIONS

### 9.1 GENERAL

All data analysis will be performed after the study is completed and the database has been locked. Statistical programming and analyses will be performed using SAS Version 9.4 or higher and R Software, Version 4.3.0 or higher. Figures will be produced using R Software, version 4.3.0 or higher. All study data will be listed by subject, and visit, as applicable, in support of summary tables.

For continuous or ordinal measures, descriptive summary statistics will include the number of observations, mean, standard deviation, median, minimum, maximum, as well as the number with results not reported. Minima and maxima will be reported with the same precision as the raw values; means and medians will be presented to 1 additional decimal place than reported in the raw values. Standard deviations will be presented to 2 additional decimal places than reported in the raw values. For categorical measures, the percentage and number of cases for each condition (e.g., subject sex, age grouping), along with a 95% Clopper-Pearson confidence interval, will be reported. The number of subjects without results will be omitted from the numerator and denominator of such calculations. All percentages will be rounded to 1 decimal place (i.e., XX.X%).

### 9.2 ANALYSIS POPULATIONS

The All-enrolled population includes all subjects who sign an informed consent form. This population will be used for disposition summaries.

The Safety population will include all subjects where the test or control IOL touched the eye.

The intent to treat (ITT) population includes all randomized subjects. Missing data will be imputed. Subjects will be analyzed as randomized. The ITT population is the primary analysis population for assessing effectiveness.

The All-implanted population includes all ITT subjects who were successfully implanted with one of the two study IOLs and who attended at least one postoperative visit. Missing data will be imputed. Subjects will be analyzed as randomized. The All-implanted population is supportive of the ITT population for assessing effectiveness.

The Per-Protocol (PP) population includes all subjects in the All-implanted population who have no major protocol deviations that could affect the interpretation of effectiveness. Exclusions from PP will be determined prior to study unmasking. Missing data will not be imputed. Subjects will be analyzed as treated. Analyses based on PP will be supportive of those based on ITT.

The Best-Case Set will include subjects in PP with all of the following characteristics:

- No major protocol deviations potentially affecting any of the primary effectiveness endpoints (BCDVA, DCNVA). Major protocol deviations that may potentially affect the primary effectiveness endpoints include, but are not limited to:
  - Inclusion of ineligible subjects
  - Implantation of incorrect IOL
  - Missed assessments for effectiveness endpoints at Form 4
  - Receipt of medication likely to interfere with visual performance at Form 4
- At least one eye implanted with a study lens
- No clinically significant preoperative ocular pathology in the first operative eye, including any of the following present prior to the operative visit
  - Pseudoexfoliation
  - Glaucoma
  - Uveitis
  - Retinal detachment
  - Diabetic retinopathy
  - Macular degeneration
  - Amblyopia
  - Other preoperative pathologies that are likely to affect central acuity
- No macular degeneration detected at any time in the first operative eye
- No previous surgery for the correction of refractive errors in the first operative eye

### 9.3 ANALYSIS SUBSETS

A best-case analysis population is defined for the testing of co-primary endpoint of BCVA logMAR of 0.3 or better at Form 4.

### 9.4 HYPOTHESES

Formal statements for the four effectiveness hypotheses are as follows.

[REDACTED]

[REDACTED]

[REDACTED]

Page 35 of 45

## 9.5 POWER AND SAMPLE SIZE

A sample size of up to 300 eyes is planned to be enrolled, where a screen failure of up to 70 eyes (23%) is anticipated. Approximately 230 eyes will be randomized and implanted with toric or control IOL.

For co-primary endpoint 3, IOL axis misalignment  $< 20^\circ$  from intended IOL axis of orientation at Form 4, we assume a success rate of 99.0% in toric lenses. Given a target of 95%, and using the testing method employed with SPE endpoints, we have 99% power to show that the upper 95% boundary of a Clopper-Pearson confidence interval of the achieved success rate includes the threshold rate of 95%.

For co-primary endpoint 4, Stability of the toric IOL axis orientation (toric IOL arm only) from Form 3 to Form 4 of  $\leq 5^\circ$  change in orientation, we assume a success rate of 91.46% in toric lenses. Given a target of 90%, and using the testing method employed with SPE endpoints, we have 99% power to show that the upper 95% boundary of a Clopper-Pearson confidence interval of the achieved success rate includes the threshold rate of 90%.

Given that all four co-primary endpoints must be met for study success, the worst-case study power, assuming independence among all tests, is  $0.94 \times 0.99 \times 0.99 \times 0.99 = 91\%$ . However, given any positive correlation among the endpoints, power will exceed 91%.

## 9.6 MULTIPLICITY

All co-primary endpoints must be met for the study to be declared a success. Consequently, no adjustment in alpha is necessary.

## 9.7 MISSING DATA AND IMPUTATION

Missing Form 4 effectiveness endpoint data will be imputed for All-implanted and ITT analyses.

For ITT, All-implanted, and PP analyses, per ANSI Z80.30-2018, eyes that have a secondary surgery that is targeted to correct for postoperative toric IOL rotation shall have their clinical results prior to that surgical intervention carried forward as the final results for analysis. Further, in cases where axis misalignment measured at follow up visits after an SSI is greater than the axis misalignment prior to SSI,

the greater misalignment error shall be considered as the final result for analysis. Repositioning of toric IOLs will result in imputation of worst observed value or assignment failure for the co-primary endpoints at Form 4 analysis, as appropriate. Imputation methods described below will retain these worst-value or failure assignments and will not overwrite them with imputed values.

The primary imputation method for all co-primary endpoints will be by multiple imputation where details of initial seed, predictors and methods will be fully described in the Statistical Analysis Plan. Co-primary endpoint 1, will use 50 imputed datasets for analysis; all other endpoints, being binary and tested by exact methods, are not amenable to combining multiple imputations, so only the first imputed dataset will be used.

In addition, for co-primary endpoint 1, where two arms are involved, a tipping point sensitivity analysis will involve initially setting all control-lens eyes with missing data to the best observed outcome (presumably, 0.0 residual cylinder) and setting all toric-lens eyes with missing data to the worst observed outcome. The best and worst values will be incremented/decremented by 0.125 D until control eyes have the worst and toric have the best value imputed. The point at which, if any, where the results of the hypothesis test changes its results regarding rejection of the null hypothesis will be reported.

For all other co-primary endpoints, the tipping-point sensitivity analysis will be performed in which missing data are initially assumed to be failures. Then, one of the imputed failures will be imputed as a success. Then, a second failure will be assigned to a success. This process will be repeated until all missing data are imputed as successes. The point at which, if any, where the results of the hypothesis test changes its results regarding rejection of the null hypothesis will be reported.

Missing data will not be imputed for PP analyses.

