## 9.8 STATISTICAL TESTING OF EFFECTIVENESS ENDPOINTS

For co-primary endpoint 1, the test of superiority of the toric lens over the control lens to result in less residual cylinder, a Wilcoxon rank-sum test will be performed, given that the distribution of residual cylinder will be discrete and likely skewed, the t-test is used only as a preliminary estimate of the needed sample size. Given the loss of power due to the use of a non-parametric test, an assumed loss of power of 5% has been made to accommodate lower power of the Wilcoxon test. The point estimate of the difference and a 95% confidence interval of the treatment effect will be provided based on the mean difference and its standard error.

For co-primary endpoints, where axis stability is examined, the upper 95% boundary of a Clopper-Pearson confidence interval will be used to test if the null hypothesis can be rejected. Number and percentage of eyes achieving various levels of stability will be summarized.

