8.4.3 Imputation Methods and Sensitivity Analyses for Co-Primary Effectiveness Endpoints

For ITT and All-implanted analyses, per ANSI Z80.30-2018, eyes that have a secondary surgery that is targeted to correct for postoperative toric IOL rotation shall have their clinical results prior to that surgical intervention carried forward as the final results for analysis. Further, in cases where axis misalignment measured at follow up visits after a secondary surgical intervention (SSI) is greater than the axis misalignment prior to SSI, the greater misalignment error shall be considered as the final result for analysis. Repositioning of test IOLs will result in imputation of worst observed value or assignment failure for the co-primary endpoints at Form 4 analysis, as appropriate. Imputation methods described below will retain these worst-value or failure assignments and will not overwrite them with imputed values.

For the ITT and All-implanted analysis populations missing co-primary endpoint data will be imputed where there are no available data at Form 4. The primary imputation method will be by

multiple imputation and be implemented using the MI and MI ANALYSE procedure in SAS® (Version 9.4 or later) or using the mice package (Version 3.16.0 or later) from R. A pre-specified seed of 20231026 (the date of version 1.0 of the protocol) will be used. Predictors will include attempted toric correction, age, and sex; 50 imputed datasets will be generated; the Markov Chain Monte Carlo (MCMC) method will be applied when using SAS. [REDACTED]

[REDACTED]

[REDACTED]

[REDACTED]

For all other co-primary endpoints, the [REDACTED] will be performed in which missing data are initially assumed to be failures. Then, one of the imputed failures will be imputed as a success. Then, a second failure will be assigned to a success. This process will be repeated until all missing data are imputed as successes. The point at which, if any, where the results of the hypothesis test changes its results regarding rejection of the null hypothesis will be reported.

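### The binary co-primary effectiveness endpoints are decided on one imputed dataset out of 50, so the interval is too narrow and the verdict near the pass mark is left to chance

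*Protocol*

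**What the plan says.** Protocol 9.7 states that "The primary imputation method for all co-primary endpoints will be by multiple imputation". It then separates the endpoints: "Co-primary endpoint 1, will use 50 imputed datasets for analysis; all other endpoints, being binary and tested by exact methods", it continues, "are not amenable to combining multiple imputations, so only the first imputed dataset will be used".

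This governs the primary result. Protocol 9.2 says that "The ITT population is the primary analysis population for assessing effectiveness", and missing data in that population are imputed. Endpoints 2, 3 and 4 carry goals of 90%, 95% and 90% of eyes (Protocol 3.1, SAP 8.4.1), and all four effectiveness endpoints must be met (Protocol 9.6, SAP 8.4). For the axis endpoints, Protocol 9.8 says that "the upper 95% boundary of a Clopper-Pearson confidence interval will be used to test if the null hypothesis can be rejected". No visible text adds between-imputation variance to that bound.

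SAP 8.4.3 fixes the seed, calls for 50 imputed datasets, and allows SAS MI "or using the mice package (Version 3.16.0 or later) from R". The text after that is redacted. The visible part does not mention a first-dataset rule. SAP section 2 says that the SAP's methods supersede the protocol's.

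Both documents plan a tipping-point analysis for the binary endpoints that runs from all missing eyes as failures to all as successes. The per-protocol analysis uses no imputation.

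**The concern.** Using dataset 1 of 50 is single stochastic imputation. It has two consequences. The imputed eyes enter the exact interval as if they had been measured, so the interval is too narrow. The point estimate, and the verdict when the result is close, also depend on one draw of the missing outcomes. Endpoint 1 is pooled over 50 datasets under the same section, so the plan treats its own co-primary endpoints unevenly.

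The stated justification does not hold. An exact test is awkward to average over imputations, but a proportion and its variance can be combined by Rubin's rules, and an interval can be built from the result. Three of the four effectiveness endpoints that must all succeed depend on this rule.

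**Working it through.** **Inputs.** 115 toric eyes and 13% non-completion (SAP 6.2): 0.13 × 115 ≈ 15 imputed, 100 observed. Endpoint 3: "we assume a success rate of 99.0% in toric lenses", target 95%. Endpoint 4: assumed 91.46%, target 90% (Protocol 9.5). The endpoint 2 test is not visible.

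**Reproducing the plan's power.** A pass means that the Clopper-Pearson upper bound reaches the target. For endpoint 4 with a one-sided 95% bound, the exact binomial power is 0.989 at n = 100 (pass mark 85) and 0.991 at n = 115 (pass mark 98). For endpoint 3 it exceeds 0.999 in both cases. The plan states 99% for each, and 0.94 × 0.99 × 0.99 × 0.99 = 0.912. The upper-bound reading is therefore the plan's own.

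**Standard error.** When imputed eyes carry no new information, the ratio of the single-dataset to the correct standard error is √(100/115) = 0.93, about 7% too small. Simulated pooling of 50 draws gave an effective sample size of about 99–100, against the 115 used by the single-dataset interval.

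**Chance that the first draw passes.** The full imputation model is not visible, so I assume a Jeffreys beta-binomial: given x successes in 100, the number K imputed as successes among 15 follows BetaBinomial(15, x + 0.5, 100 − x + 0.5). The first dataset passes if x + K reaches the pass mark.

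Example: x = 85, endpoint 4, pass mark 98. K must be at least 98 − 85 = 13, and P(K ≥ 13) = 0.59.

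Protocol 9.5 ties endpoints 3 and 4 to the SPE method, which SAP 8.5.1 describes with a one-sided 95% limit. Sidedness is not fully settled in the visible text, so both versions are shown.

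| Target | Bound | Pass mark of 115 | Observed of 100 | P(first draw passes) |
|---|---|---|---|---|
| 90% | one-sided 95% | 98 | 84 / 85 / 86 | 0.29 / 0.59 / 0.83 |
| 90% | two-sided 95% | 97 | 83 / 84 / 85 | 0.26 / 0.55 / 0.80 |
| 95% | one-sided 95% | 105 | 90 / 91 / 92 | 0.22 / 0.59 / 0.86 |
| 95% | two-sided 95% | 104 | 89 / 90 / 91 | 0.18 / 0.54 / 0.83 |

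**After pooling.** For 50 draws, let Q be the mean proportion and T = mean within-variance + (1 + 1/50) × between-variance. The effective sample size is Q(1 − Q)/T, and a Clopper-Pearson bound is taken at that size. With one-sided 95% bounds the pass probabilities become 0.02 / 1.00 / 1.00 at 84 / 85 / 86 and 0.00 / 0.95 / 1.00 at 90 / 91 / 92. Pooling removes nearly all the randomness.

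**How often it matters.** If π(x) is the pass probability above, two independent first draws disagree with probability 2π(x)(1 − π(x)), averaged over x ~ Binomial(100, p).

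- Endpoint 4 at 91.46%: 0.021 (one-sided 95%) and 0.012 (two-sided 95%). SAP 8.5.1 also cites one-sided alpha 0.10, which gives 0.033.
- Endpoint 3 at 99%: below 0.0001 in every version.
- True rate near the boundary (85–86% for endpoint 4, 90–92% for endpoint 3; one-sided 95%): 0.14–0.15.

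**Range by missingness** (one-sided 95%). The number of observed counts at which the first draw passes with probability between 0.05 and 0.95 is 2 for each endpoint with 6 eyes missing; 3 (endpoint 3) and 5 (endpoint 4) with 15 missing; 4 and 5 with 23 missing.

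**The case against.** The strongest reply is that little turns on this. The seed is fixed in advance, so nobody can choose among draws within one program. A single-arm binary verdict depends only on how many missing eyes are imputed as successes. The tipping-point analysis runs through every such number, so all 50 datasets lie on its grid and any fragility would be reported. At the planning rates the verdict almost never depends on the draw. The SAP, which takes precedence, may already pool behind the redaction.

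Most of this stands, and it limits the size of the point. It does not remove it. A fixed seed makes an arbitrary draw repeatable, and the same seed gives different draws in SAS and in mice, both of which SAP 8.4.3 allows. The tipping-point analysis is supportive, so the primary rate, bound and verdict still come from one dataset. The redaction means that the rule is confirmed for the protocol only; if the SAP does pool, Protocol 9.7 needs aligning.

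A reader might infer that the narrow interval favours the device. Under the plan's rule it does not: the upper bound must reach the target, so a shorter interval makes passing slightly harder. It would favour the device only under a lower-bound rule. A reader might also infer that the trial's outcome as a whole is arbitrary. The planning-rate figures do not support that.

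**Conclusion.** The rule as written in Protocol 9.7 is wrong for the binary co-primary effectiveness endpoints, and its stated reason is incorrect. Whenever data are missing, the reported interval overstates precision, with a standard error about 7% too small at 13% missing. Near the pass mark the verdict is a matter of chance; elsewhere it is not affected in practice. This should be corrected, but it does not threaten the study at its planning assumptions.

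The figures assume 15 of 115 toric eyes missing, a Jeffreys beta-binomial imputation model without informative predictors, and the plan's upper-bound rule. They cover endpoints 3 and 4. Endpoint 2 falls under the same sentence, but its test is not visible. The safety endpoints are outside the point, since SAP 8.1 does not impute safety data.

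**What to change.** - Analyse all 50 imputed datasets for the binary effectiveness endpoints and pool the proportion by Rubin's rules.
- Apply the decision rule to a multiple-imputation Wilson limit, or to a Clopper-Pearson limit at the pooled effective sample size. State the sidedness.
- Make sure that the limit is defined at 100% success. At the assumed 99%, all 100 observed eyes succeed with probability 0.99^100 = 0.37, and all of 115 with 0.99^115 = 0.31. Uncorrected logit pooling fails there. The effective-size formula becomes 0/0 if every imputed dataset is all successes, so it needs a stated convention, such as using the number of eyes actually observed.
- Name one imputation procedure and package in advance.
- Keep the tipping-point analysis, and add complete-case Clopper-Pearson as a sensitivity analysis.
- Align Protocol 9.7 with SAP 8.4.3.

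The cost is a wording change in both documents and a few lines of code. The pooled limit is not strictly exact, but neither is an exact limit computed on imputed eyes.
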